9.6.1.2 Analysis Methods

The primary analysis of ORR will be conducted on the all treated population. A descriptive analysis will be done on for subgroups of subjects who receive acalabrutinib alone or the combination of acalabrutinib and pembrolizumab. ORR and the corresponding 90% and 95% two-sided CI calculated using exact method to the binomial distribution will be presented.

The number and proportion of subjects within each category of response as well as the associated 95% CIs will be presented. The proportion will be estimated by dividing the number of subjects within each category of response by the total number of subjects in the analysis population. Each subject will be counted within only one response group, with the best response during the study as the classification group.

In addition, for subjects with CLL/SLL in Parts 1 and 2, a response will be assessed according to Table 4-2, which reflects modified International Working Group response criteria (Hallek 2008) as recently updated (Cheson 2012) to include PRL. For the purpose of this analysis, lymphocytosis at a given timepoint will be defined as absolute lymphocyte count which is above normal limits and is not \geq 50% decreased from baseline. For Part 3 subjects with MF, an additional analysis will evaluate response when defined as CR + PR only.

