All subjects will have bone marrow biopsy, hematology, chemistry, thyroid, and urinalysis safety panels performed at screening. Once dosing commences (Day 1), all subjects will be evaluated for safety, including serum chemistry, hematology, and thyroid function tests, once weekly for the first 8 weeks, followed by a Week 10 visit and then every 3 weeks

thereafter (every 6 weeks thereafter for thyroid function tests) through Week 103. For subjects who discontinue pembrolizumab at Week 103, the Week 103 visit will be followed by Week 106 and Week 109 visits, at which time, the investigator will determine eligibility to continue single-agent acalabrutinib treatment. Subjects remaining on study treatment after Week 103 will have a Week 103 and Week 115 visit, and then visits for safety and tumor response assessments every 24 weeks starting at Week 127 through 3 years (for subjects with CLL/SLL histologies) or 5 years (for subjects with non-CLL/SLL histologies [i.e., DLBCL/Hodgkin lymphoma]), and then every 52 weeks thereafter (all histologies).

[figure not shown]
Subjects who permanently discontinue pembrolizumab at any time during study participation must have a minimum of 2 consecutive study visits, 3 weeks apart, after the last dose of pembrolizumab for safety evaluation. The study visits will be scheduled as follows:

- For all subjects except MM and CLL subjects
  - If a subject discontinued pembrolizumab prior to completing 37 weeks on study and is on acalabrutinib alone, study visits will be held every 3 weeks until Week 37. After Week 37, study visits will be held every 12 weeks.
  - If a subject discontinued pembrolizumab after completing 37 weeks on study and is on acalabrutinib alone, 2 consecutive study visits will be held 3 weeks apart (e.g., Week 40 and 43), after which study visits will be held every 12 weeks.
  - It is acknowledged that the discontinuation timepoint of pembrolizumab (if applicable) is unique per subject. To synchronize the every 12-week study visit schedule with the radiologic tumor assessment schedule, the first 2 study visits after pembrolizumab discontinuation should be 3 and 6 weeks after pembrolizumab discontinuation and then scheduled to align with the nearest radiological timepoint.
- For CLL subjects

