## Figure 4 Study Schema

ACP-196=acalabrutinib; BID=twice per day; CLL/SLL= chronic lymphocytic leukemia/small lymphocytic lymphoma; DLT=dose-limiting toxicity; FL= follicular lymphoma; GCB=germinal center B-cell diffuse large B-cell lymphoma; iNHL=indolent non-Hodgkin lymphoma; IV=intravenous; MF=myelofibrosis (per Amendment 3, Part 3, MF was not opened for this study); MM=multiple myeloma; non-GCB DLBCL=non-germinal center B-cell diffuse large B-cell lymphoma; PO=oral; Q3W=every 3 weeks; RS=Richter's syndrome (under Amendment 4, subjects with RS are no longer enrolled); WM=Waldenström macroglobulinemia.

[figure not shown]

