# 5.5.4 Analysis of Efficacy Parameters

#### **Response Rate**

The individual and composite endpoints of response and progression will be determined. Tumor control will be documented at each assessment by response category (see Section 4.2) as defined for each response parameter, date that response is first documented, and date of disease progression.

ORR will be defined as the proportion of subjects who achieve a response of PR or CR (see Section 4.2). For Part 3 subjects with MF, ORR will be defined as the proportion of subjects who achieve a response of clinical improvement or better (clinical improvement, PR, or CR) as shown in Table 9. ORR will be calculated and the corresponding exact 2-sided 90% and 95% CIs will be derived.

In addition, for subjects with CLL/SLL in Parts 1 and 2, a response will be assessed according to Table 6, which reflects modified International Working Group response criteria (Hallek 2008) as recently updated (Cheson 2012) to include PRL. For the purpose of this analysis, lymphocytosis at a given timepoint will be defined as absolute lymphocyte count which is above normal limits and is not ≥50% decreased from baseline.

For Part 3 subjects with MF, an additional analysis will evaluate response when defined as CR + PR only. A descriptive analysis will be done on the subgroups of subjects with MF who receive acalabrutinib alone or the combination of acalabrutinib and pembrolizumab.

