9 STATISTICAL METHODS OF ANALYSIS

9.1 General Principles

Descriptive statistics will be used to summarize baseline demographic and disease characteristics, study drug administration, efficacy and safety outcomes. Descriptive summaries of discrete data will present the sample size and the incidence as a frequency and as a percentage. Descriptive summaries of continuous data will present

the sample size, group mean, standard deviation (SD), median, and range. Confidence intervals (CIs) may be included as appropriate.

Summary tables will be presented by disease types: CLL/SLL, MCL, WM, FL, GCB DLBCL, MM, non-GCB DLBCL, RICHTER's and Other (include unclassifiable DLBCL, double hit lymphoma, FL with transformation, mediastinal DLBCL, mediastinal gray zone lymphoma, non-hodgkin's lymphoma [NHL], non-mediastinal gray zone lymphoma, red pulp small B-cell lymphoma, triple hit high grade NHL, hodgkin's lymphoma, marginal zone lymphoma), unless otherwise stated.

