10 CHANGES FROM PROTOCOL-SPECIFIED ANALYSES

There is no major change from protocol-specified analyses.

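### SAP 9.6.1.2 drops the myelofibrosis restriction from the acalabrutinib-alone versus combination ORR split, leaving undefined subgroups that no regimen in Parts 1 and 2 supports

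*SAP*

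**What the plan says.** Protocol 5.5.4, under Response Rate, confines the split to one disease: "A descriptive analysis will be done on the subgroups of subjects with MF who receive acalabrutinib alone or the combination of acalabrutinib and pembrolizumab". SAP 9.6.1.2 carries the sentence over as "A descriptive analysis will be done on for subgroups of subjects who receive acalabrutinib alone or the combination of acalabrutinib and pembrolizumab". It now stands between the statement that the primary ORR analysis uses the all-treated population and the statement on exact 90% and 95% confidence intervals. The same SAP section keeps the restriction for a different analysis: "For Part 3 subjects with MF, an additional analysis will evaluate response when defined as CR + PR only".

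On whether any MF subjects exist, the legend to Protocol Figure 4 says: "per Amendment 3, Part 3, MF was not opened for this study". Elsewhere both documents say that Part 3 is closed to enrollment. The SAP's reporting groups leave MF out: "Summary tables will be presented by disease types: CLL/SLL, MCL, WM, FL, GCB DLBCL, MM, non-GCB DLBCL, RICHTER's and Other".

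SAP Section 10 states: "There is no major change from protocol-specified analyses".

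**The concern.** The protocol's split had a planned regimen behind it. In Part 3 some subjects were to stay on acalabrutinib alone after a run-in and others were to add pembrolizumab. Without the MF limit, the SAP asks for the same split among subjects who were all scheduled to receive both drugs, and it does not say who belongs in which group.

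The study has no comparator. A table that sets an ORR for acalabrutinib alone beside one for the combination could be taken as evidence of what pembrolizumab adds. If membership depends on what happened after treatment began, and partly on response, the two rates cannot carry that meaning.

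**Working it through.** No figure in the plan is in dispute. The check is a comparison of text, followed by a hypothetical calculation of what the second reading below could do.

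**1. What changed.** The protocol and SAP sentences differ in substance only by the loss of the MF qualifier. Because the qualifier survives later in the same SAP section for the CR + PR analysis, a programmer has no textual reason to read it back into the earlier sentence. As written, the split applies to all treated subjects.

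**2. Who could be on acalabrutinib alone.**
- Part 3: the only planned route (Protocol 3.0 and 3.5), but not opened.
- Parts 1 and 2: Protocol Appendix 5 schedules both drugs from Week 1. Acalabrutinib alone arises only if pembrolizumab is never given or is stopped. The protocol foresees stopping in its visit rules: "If a subject discontinued pembrolizumab prior to completing 37 weeks on study and is on acalabrutinib alone".
- The stated reasons (Protocol 3.0, All Parts) are pembrolizumab toxicity or another AE; confirmed CR (sCR in MM) after at least 24 weeks of treatment plus two further doses; and completion of the 103-week course, which requires tolerating the drug without progression.

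**3. Two ways to program the undefined groups.**
- *Ever received.* Anyone with at least one pembrolizumab infusion counts as combination. Since both drugs start in Week 1, the alone group should be nearly empty, and the combination row nearly repeats the all-treated ORR.
- *Stopped pembrolizumab and continued acalabrutinib.* Membership is then fixed after baseline. SAP 9.6.1.2 classifies each subject by best response over the whole study, whatever drugs were being taken when it occurred. A CR reached on the combination, followed by an end to pembrolizumab, could be counted under acalabrutinib alone.

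**4. Hypothetical size under the second reading.** Suppose everyone has the same true ORR, p. Let a be the probability that a responder is classed as alone, and b the same probability for a non-responder. Then

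ORR(alone) = pa / [pa + (1 − p)b]

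ORR(combination) = p(1 − a) / [p(1 − a) + (1 − p)(1 − b)]

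The value p = 0.20 is the minimum ORR of interest in Part 2 (Protocol 5.2); p = 0.40 is an assumed alternative. The values of a and b are assumptions, because the documents give neither.

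| p | a | b | Alone | Combination |
|---|---|---|---|---|
| 0.20 | 0.1 | 0.1 | 20.0% | 20.0% |
| 0.20 | 0.5 | 0.1 | 55.6% | 12.2% |
| 0.20 | 0.1 | 0.3 | 7.7% | 24.3% |
| 0.40 | 0.5 | 0.1 | 76.9% | 27.0% |
| 0.40 | 0.1 | 0.3 | 18.2% | 46.2% |

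For the second row: alone = 0.10 / (0.10 + 0.08) = 0.556; combination = 0.10 / (0.10 + 0.72) = 0.122. For the third: alone = 0.02 / (0.02 + 0.24) = 0.077; combination = 0.18 / (0.18 + 0.56) = 0.243.

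With no difference between treatments, the gap at p = 0.20 is about +43 points if responders stop pembrolizumab more often and about −17 points if non-responders do.

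**The case against.** The strongest reply is that this is a drafting slip with little consequence. The SAP sentence is visibly garbled, which suggests that words were lost in transfer. The analysis is labelled descriptive, SAP Section 5 plans no formal test, the primary objective is safety, no decision rule uses the split, and the all-treated ORR does not change. All of that stands and limits the weight of the point.

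Four stronger readings are tempting, and the documents do not support them.

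- *That the groups are set by who stopped pembrolizumab.* The SAP never says so. The ever-received reading is at least as natural, and it produces a nearly empty group rather than a biased one.
- *That the alone group would consist of subjects still benefiting, so its ORR would be inflated.* Toxicity and AEs are also named reasons for stopping, and ending pembrolizumab after a confirmed CR is optional. Protocol 1.4.2.1 reports 13 subjects who discontinued treatment for AEs attributed only to pembrolizumab, though not how many stayed on acalabrutinib. It gives a median exposure of 3.4 months at the September 2017 cutoff. Twenty-four weeks is about 5.5 months (168 / 30.4), so at that cutoff most subjects had not reached the point at which the CR rule could apply. Nor do the documents give a response rate for anyone never infused.
- *That the MF split would have been a sound comparison.* It would not. MF subjects were to stay on monotherapy if the investigator saw a meaningful response after the six-week run-in, so that group too was selected after baseline on response. Restoring the limit helps because the group is empty.
- *That Section 10 is plainly false, or that the split was widened deliberately.* Section 10 disclaims only major changes, and one added descriptive subgroup may not count as major. The SAP is dated January 2020, after enrollment closed in May 2017, but nothing shows intent.

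**Conclusion.** The concern holds in a limited form. SAP 9.6.1.2 calls for an ORR split that the protocol planned only for MF, that no regimen in Parts 1 and 2 supports, and whose groups are undefined. Section 10 does not record the change. The output would be either close to uninformative or subject to bias from membership decided after baseline. The documents settle neither which of these would occur nor, in the second case, the direction or amount of bias. The percentages worked out above show only that a large gap in either direction is possible without a treatment difference; they are not estimates for this trial.

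The conclusion rests on two assumptions: that the Figure 4 legend is right that Part 3 was not opened, and that Protocol Amendment 6, which SAP Section 1 says it implements, carries the same MF-only sentence as the protocol supplied. It is a worthwhile correction to a secondary, descriptive output and does not threaten the primary ORR analysis.

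**What to change.** In SAP 9.6.1.2, either delete the sentence, or restore its restriction to subjects with MF and add that the analysis is not performed because Part 3 was not opened. For Parts 1 and 2, report ORR by disease type on all treated subjects only, with no split by acalabrutinib alone or combination.

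If the sponsor does intend such a split, the SAP must state the rule for assigning subjects and list the addition in Section 10.

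The cost is one edited sentence and one table fewer. No new data are needed.

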#### All Parts

Treatment with acalabrutinib may be continued until disease progression or an unacceptable drug-related toxicity occurs as defined in the protocol. Treatment with acalabrutinib can continue until the end of trial, defined as 48 months after the last subject is enrolled. Subjects who are still on treatment at the end of the study and deriving clinical benefit from acalabrutinib treatment may be eligible to enroll in a separate rollover study of acalabrutinib monotherapy. In the event that a rollover or safety extension study is available at the time of the final data cutoff and database closure, subjects who remain in Study ACE-LY-005 may be transitioned to such a study. Once all active subjects are eligible for and move to a rollover or safety extension study would ensure treatment continuation, with visit assessments per the rollover or extension protocol. Any subject who would be proposed to move to a rollover or safety extension study would be asked to sign an Informed Consent Form (ICF) for the rollover or safety extension study.

Treatment with pembrolizumab may continue for 24 months (103 weeks) from first dose of pembrolizumab, provided subjects are tolerating the drug and not progressing. In addition, pembrolizumab treatment can end for subjects with confirmed CR (or sCR for MM) if treatment has been administered for at least 24 weeks and 2 doses of pembrolizumab have been administered after confirmation of CR/sCR. Subjects who have **confirmed** progressive disease will come off treatment. Note: If there is uncertainty regarding whether there is cancer progression, the subject may continue study treatment and remain under close observation (e.g., evaluated at 4- to 8-week intervals) pending confirmation of progression. In particular, transient worsening of disease during temporary interruption of study therapy (e.g., for drug-related toxicity or intercurrent illness) may not indicate disease progression. In such circumstances, and if medically appropriate, subjects may resume therapy and relevant clinical, laboratory, and/or radiographic assessments should be done to document whether tumor control can be maintained or whether actual disease progression has occurred.

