#### Table 8Response Criteria for MM (incorporating EBMT and IMWG)

EBMT: Bladé 1998; IMWG: Durie 2006.

EBMT=European Group for Blood and Marrow Transplant; FLC=(serum) free light chains; IMWG=International Myeloma Working Group; MM=multiple myeloma.

Note: \* Note clarification to IMWG criteria for coding CR and VGPR in subjects in whom the only measurable disease is by serum FLC levels: CR in such subjects a normal FLC ratio of 0.26-1.65 in addition to CR criteria listed above. VGPR in such subjects is defined as a >90% decrease in the difference between involved and uninvolved free light chain FLC levels

- a. All response categories require 2 consecutive assessments made at ≥4 weeks after the start of study therapy and any time before the institution of any new therapy after study therapy; CR and PR and SD categories also require no known evidence of progressive or new bone lesions if radiographic studies were performed. Radiographic studies are not required to satisfy these response requirements.
- b. Confirmation with repeat bone marrow biopsy not needed
- c. Presence/absence of clonal cells is based upon the kappa/lambda ratio. An abnormal kappa/lambda ratio by immunohistochemistry and/or immunofluorescence requires a minimum of 100 plasma cells for analysis. An abnormal ratio reflecting presence of an abnormal clone is kappa/lambda of >4:1 or <1:2.
- d. All relapse categories require 2 consecutive assessments made at any time before classification as relapse or disease progression and/or the institution of any new therapy.
- e. For progressive disease, serum M-component increases of ≥1 gm/dL are sufficient to define relapse if starting M-component is ≥5 g/dL.
- f. Relapse from CR has the 5% cutoff versus 10% for other categories of relapse.
- g. For purposes of calculating time to progression and progression-free survival, CR subjects should also be evaluated using criteria listed above for progressive disease.

Response Categories	Required Criteria (for all response categories, benefit must last for ≥12 weeks to qualify as a response)

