9.6 Analyses of Efficacy Endpoints

9.6.1 Response Rate

9.6.1.1 Definition

ORR will be defined as the proportion of subjects who achieve a response defined in Section 4.2 in protocol for different disease. For lymphoma, response means partial response (PR) or better, for WM subjects response means minor response (MR) or better, for subjects with MF, response including clinical improvement or better (clinical improvement, PR, or CR). Please refer to Protocol section 4.2 for the detail information and definition of the response.

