9.6.2 Duration of Response

The duration of overall response (DOR) defined as the interval from the first documentation of response to the earlier of the first documentation of definitive disease progression or death from any cause. Subjects who had the event after the start of subsequent therapy, or are progression-free and alive at the time of data cutoff, or have unknown status will be censored at the last tumor assessment on or before the start of subsequent therapy and data cut-off time. The censoring rules for DOR are summarized in [Appendix 12.2](#). The summary of DOR including mean, minimum, maximum, Q1 and Q3 are provided for all the responders for each disease group.

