12.2 Censoring Rules for Duration of Response

Situation	Outcome	Date	Event Description/ Censoring Reason
Progression documented between scheduled visits on or before receiving subsequent anticancer therapy or data cutoff, whichever occurred first	Event	Earliest date of disease assessment documenting progression	PD
Death without documented PD on or before receiving subsequent anti-cancer therapy or data cutoff, whichever occurred first	Event	Date of Death	Death
New anti-cancer treatment Started before PD or death for subjects with or without documented PD or death and before data cutoff	Censored	Date of last adequate disease assessment prior to subsequent anti-cancer treatment	New anti-cancer therapy
No documented PD or death at the time of data cutoff and subject not received subsequent anti-cancer therapy or subsequent anti-cancer therapy start date after the data cutoff	Censored	Date of last adequate disease assessment on or before data cutoff	Data cutoff
Withdrew consent before documented PD or death	Censored	Date of last adequate disease assessment	Withdrew consent
Lost to follow-up before documented PD or death	Censored	Date of last adequate disease assessment	Lost to follow-up

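### Best response in SAP 9.6.1.2 has no stop at progression, so a subject who first responds after a recorded progression counts for ORR but has a PFS event and a negative DOR

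*SAP*

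**What the plan says.** **Response.** SAP 9.6.1.1 states: "ORR will be defined as the proportion of subjects who achieve a response defined in Section 4.2 in protocol for different disease". Protocol 5.5.4 (Response Rate) states: "ORR will be defined as the proportion of subjects who achieve a response of PR or CR". Neither gives a time limit. SAP 9.6.1.2 then sets the classification: "Each subject will be counted within only one response group, with the best response during the study as the classification group".

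**Duration of response.** SAP 9.6.2 defines it as the "interval from the first documentation of response to the earlier of the first documentation of definitive disease progression or death from any cause". In SAP 12.2 the event date is the "Earliest date of disease assessment documenting progression". If new treatment starts first, the subject is censored at the "Date of last adequate disease assessment prior to subsequent anti-cancer treatment". SAP 9.6.6 puts every responder into the DOR analysis.

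**PFS.** SAP 12.3 uses the same event date and the same censoring at new therapy as SAP 12.2.

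**Treatment during uncertain progression.** Protocol 3.0 (All Parts) says that, where progression is in doubt, "the subject may continue study treatment and remain under close observation" until it is confirmed. Protocol 3.6 and SAP 3.1 repeat this. Protocol 3.8 adds that a hold of only a week may produce temporary worsening.

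**Limit on response in one disease.** For multiple myeloma, Protocol Table 8, footnote a, requires the response assessments to fall at "any time before the institution of any new therapy after study therapy". It sets no limit at progression.

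**The concern.** Three endpoints describe the same subject but do not share an observation window. PFS and DOR close at the first documented progression. ORR stays open until the end of the study. Nothing in SAP 9.6.1, 9.6.2 or 9.6.6 requires the response to come before the progression that ends it.

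The order that causes trouble is foreseeable, because the protocol expects some subjects to worsen, stay on study treatment and be assessed again. If the worsening was recorded as progressive disease and the subject then responds for the first time, the written rules give a DOR whose end date precedes its start date. The programmer must then choose a repair after seeing the data: drop the subject from DOR, move the progression date, or withdraw the response. Each choice changes a reported efficacy result.

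**Working it through.** **Inputs**

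- Cohort size n = 30, and 20% as the lowest ORR of interest (SAP 3.2; Protocol 5.2).
- Stated one-sided exact 90% upper bound for 2 responders in 30: 16.8% (same sections).
- Imaging at Week 8, at Week 19, then every 12 weeks (Protocol Appendix 5).
- Re-evaluation of uncertain progression at, for example, 4 to 8 weeks (Protocol 3.0, All Parts).

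**1. The plan's own figure.** The exact upper bound for x responders is the 90th percentile of a Beta(x + 1, n − x) distribution. For x = 2 this is Beta(3, 28), which gives 16.8%. The stated figure is reproduced.

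**2. One subject under the written rules.** Suppose progression is recorded at Week 8 and the first partial response at Week 19.

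| Endpoint | Rule | Result |
|---|---|---|
| PFS | Earliest documented progression (SAP 12.3) | Event at Week 8 |
| ORR | Best response over the study (SAP 9.6.1.2) | Responder |
| DOR | First response to earliest progression (SAP 9.6.2, 12.2) | 8 − 19 = −11 weeks |

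If the response is instead seen at a re-evaluation 4 to 8 weeks after Week 8, the dates are Week 12 to Week 16. DOR is then 8 − 12 = −4 weeks to 8 − 16 = −8 weeks. The sign does not depend on the spacing chosen.

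**3. Effect on ORR.** One subject in 30 is 1/30 = 3.3 percentage points. Take a cohort with two responses before progression and, by assumption, one after it:

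- Counting all three: 3/30 = 10.0%. The upper bound, from Beta(4, 27), is 20.9%, so 20% is not excluded.
- Counting two: 2/30 = 6.7%. The upper bound is 16.8%, so 20% is excluded.

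**4. Range under assumed rates.** Let the true response rate before progression be 5%, and let a share f of the other subjects have a later response. The counted rate is 0.05 + 0.95f.

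| f | Counted rate | P(at least 3 of 30) |
|---|---|---|
| 0% | 5.0% | 0.19 |
| 2% | 6.9% | 0.34 |
| 5% | 9.75% | 0.57 |
| 10% | 14.5% | 0.83 |

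Both the 5% and the values of f are assumptions.

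**5. The new-therapy route.** If the last adequate assessment before new therapy is at Week 8 and a response is recorded at Week 19, the censored DOR is also −11 weeks. This needs a tumour assessment after new therapy. The radiology row of Protocol Appendix 5 shows none at early termination, safety follow-up or the 12-weekly follow-up.

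**The case against.** The strongest reply is that an uncertain progression is not a progression. The protocol keeps a subject on treatment only while there is doubt, and takes confirmed progressors off. SAP 9.6.2 speaks of definitive progression and SAP 9.6.3 of objective progression. On that reading a doubtful Week 8 scan followed by a response is no event, and nothing conflicts. This stands in part: the conflict needs the doubtful assessment to be recorded as progressive disease. But neither adjective is defined, and the tables in SAP 12.2 and 12.3 take the earliest documenting assessment without asking for confirmation.

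Some disease criteria narrow the problem further. Myeloma progression needs two consecutive assessments (Table 8, footnote d). In Waldenström macroglobulinemia, the IgM rise must be confirmed (Table 7). In CLL, isolated treatment-related lymphocytosis is not progression unless symptomatic (Table 6, footnote a). The lymphoma criteria in Table 5 carry no such general requirement.

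A reader might infer that responses to later therapy will be credited to the study drugs just as readily. The documents do not support that. Starting other anticancer therapy is a listed reason for withdrawal from study treatment (Protocol 3.11), no follow-up imaging is visible in the readable schedule, and the myeloma table already excludes such responses. Because the footnote to the radiology row is not in the readable text, this route cannot be fully checked and should be treated as secondary.

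Finally, ORR is a secondary, descriptive measure, and SAP 5 plans no formal test. That limits the weight of the point. It does not remove the inconsistency between the three rules.

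**Conclusion.** The point holds in a conditional form. As written, the SAP allows one subject to have a PFS event, a later first response that counts for ORR, and a negative DOR. This happens if an assessment is recorded as progressive disease, the subject remains under assessment, and a first response follows. The protocol makes that order foreseeable, and no stated rule resolves it.

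Each such subject adds 3.3 points to ORR in a cohort of 30. At the 2-versus-3 margin, one is enough to move the upper bound across the 20% benchmark (16.8% to 20.9%). The size of the negative duration depends on the illustrative dates.

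A reader might go further and infer that ORR is inflated or that negative durations will occur. The documents do not show this: they give no count of subjects with this sequence, and none may exist. The primary safety objective and the stated sample-size figures are unaffected. This is an inconsistency worth settling in the SAP, not a threat to the trial's main conclusion.

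**What to change.** - **SAP 9.6.1.2:** define best overall response as the best response from first dose to the earliest of the progression date used for PFS and DOR, the start of subsequent anticancer therapy, and data cutoff.
- **SAP 9.6.2, 9.6.3, 12.2 and 12.3:** state one progression date for all three endpoints. Say whether an uncertain progression that is not later confirmed counts as progressive disease. Without this, the new cut-off could remove responses in the very subjects whom the protocol keeps on treatment pending confirmation.
- **Reporting:** list responses after that date separately, so that they remain visible.

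The cost is a few sentences of SAP text and no new data. ORR may fall slightly.
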